each. Detailed information will be collected on reported adverse events (AEs) of special interest including hypersensitivity reactions, loss of drug effect, renal impairment, neurocognitive disorders, inhibitor development, and serious adverse events (SAEs). These parameters will assess if there are any potential safety risks of long-term PEG exposure. The AEs of hypersensitivity and loss of drug effect are related to the class of FVIII replacement therapy. Since damoctocog alfa pegol is a PEGylated product, immunogenicity related to the PEG component can occur. Although the 60 kDa PEG that is part of the damoctocog alfa pegol molecule is larger than the 20-40 kDa PEG moieties on other FVIII replacement products, the low content of PEG associated with the site-specific PEGylation of damoctocog alfa pegol results in a lower PEG load (PEG amount per treatment or per week) and consequently in plasma and tissues relative to some other PEGylated products. The preclinical toxicology studies demonstrated an absence of any pathological effects. The low peak plasma level of approximately 0.1 mg/L at steady state in humans is consistent with these pre-clinical data. No increase in PEG plasma levels has been observed in the clinical studies including the extension studies in more than 100 patients with a total treatment period of at least 3 years up to 6 years¹.

The results of this observational study aim to add to the knowledge of the safety profile of real-world prophylaxis with damoctocog alfa pegol.

Prior to finalization of the present HA-SAFE protocol v1.0, protocol version 0.5 was endorsed by the PRAC on 28 November 2019 (as confirmed in the outcome letter dated 05 December 2019).

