9.1.2 Secondary endpoints

The secondary endpoints are:

- Number of ARs that are defined within the system organ classes nervous system and psychiatric disorders from study start to end of the study
- Number of ARs related to hepatic or renal function from study start to the end of the study
- Change in kidney and liver function parameters from study start to the end of the study
- Change in PEG-plasma levels from study start to the end of the study
- Number of patients with abnormal findings as assessed by neurological examination across all age groups from study start to the end of the study

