9.2.4 Representativeness

The eligibility criteria have been selected to allow for a broad representation of patients within the study. The study will enroll previously treated hemophilia A patients initiating or currently receiving prophylaxis damoctocog alfa pegol. Prophylaxis therapy is the recommended standard of care for patients with severe disease and those with moderate disease with a severe patient bleeding profile. By enrolling all eligible patients with mild, moderate or severe disease consecutively, the study will capture real-world data.

Previously untreated hemophilia A patients are not eligible for this study as the safety of damoctocog alfa pegol in this patient population has not been established. Given the incidence rate of hemophilia A, 1 in 5,000 live male births, previously untreated patients represent approximately 2% of the hemophilia patient population. Thus, the study population is broadly representative of mild, moderate, and severe hemophilia A patients, even when previously untreated patients are excluded.

In addition, the inclusion of a representative sample of study sites (i.e., health care providers, hospitals, etc.) in terms of geography, practice size, and academic or private practice type is aimed as a measure to enhance the generalizability of study results. Nevertheless, the final sample of study sites will strongly depend on the willingness of physicians to participate in the study.

The patients documented in the study should be selected based only on eligibility according to a minimal set of selection criteria (see sections 9.2.1.1 and 9.2.1.2). No further selection should be

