9.2.5 Visits

The physician documents a first visit that corresponds to the initiation of the observational period (initial visit/baseline) in the eCRF/EDC system. Follow-up visits occur during routine practice – in this non-interventional study, the exact referral dates for those visits are not defined in the study protocol. After the initial visit, data collection will continue for a minimum of 48 months. Data collection will continue after 48 months for those patients who are still within the overall study period (for patients initiating follow-up in the first years of the study). Each visit or assessment, as well as each AE, recorded in the patient diary is to be documented in the eCRF/EDC system. The data to be collected, where they are available as part of routine practice, are summarized in [Table 2](#).

Enrollment/Initial visit

Once a patient is deemed eligible for inclusion, the physician will inform the patient and legal representative (where applicable) about the study. If the patient is interested in participating, the physician will ask the patient (and, if appropriate, the legal representative) to sign the informed consent form (see section [10.4](#)). After patients have been enrolled in the study, baseline information is recorded during this initial visit.

Follow-up data collection period

The follow-up assessments will be completed in the eCRF/EDC system. These assessments do not require the scheduling of any additional visits outside of the standard of care.

Due to the observational nature of the study, no specific follow-up visits can be scheduled, and it is unknown when a patient will come for the next visit. Thus, data collection will occur continuously throughout the patient's observational period, i.e. each visit or assessment is to be documented in the eCRF/EDC system.

In case a patient is seen by more than one physician (e.g., the patient is monitored by a physician other than the initial treating physician), the initial treating physician should make every effort to collect information on visits that took place (and results that were obtained) outside the treating physician's site. For example, by communicating with the other physician or by having the patient/legal representative obtain a letter with detailed information and results (e.g. ARs, medications given, procedures performed).

End of observation and final safety follow-up

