9.7 Data analysis

9.7.1 Statistical considerations

Statistical analyses will be of an explorative and descriptive nature. The study is not aimed to confirm or reject predefined hypotheses; hence no formal hypothesis testing will be performed.

All variables will be analyzed descriptively with appropriate statistical methods: categorical variables by frequency tables (absolute and relative frequencies) and continuous variables by sample statistics (i.e., mean, standard deviation [SD], minimum, median, quartiles, and maximum). Continuous variables will be described by absolute value and as change from baseline per analysis time point, if applicable.

All analyses will be performed for the total study population (overall analysis).

Sample size and disposition information including reasons for discontinuation by analysis time point will be displayed in a frequency table.

All therapies documented in the following forms will be coded using the World Health Organization Drug Global.

- Prior and concomitant medication

Any diagnoses/diseases/event terms documented in the following forms will be coded using the latest Medical Dictionary for Regulatory Activities (MedDRA) version:

- General medical/surgical history
- Adverse events

Interim reports will be provided annually to the competent authorities as specified in the milestones. The final analysis will be performed after the end of the study, which is the date the analytical dataset is completely available.

All statistical details including calculated variables and proposed format and content of tables will be detailed in the Statistical Analysis Plan (SAP). Bayer Consumer Care AG will provide oversight of data analysis activities that will be assigned to a CRO. All specific processes and technical details will be documented by the CRO statistician in the SAP and tables specification manual. The SAP will be finalized before the first database lock. The SAP will be available upon request (see [Table 3](#)).

Analysis populations:

The Safety Analysis Set (SAF) include all patients who took at least 1 dose of damoctocog alfa pegol in the study

Missing data:

Because the aim of this study is to obtain data under conditions of routine clinical care (i.e., naturalistic settings), some patients may have missing values for some variables. To address missing data, the following strategy will be applied:

- In general, clinical outcomes collected in the study will not be imputed.

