9.7.4 Analysis of secondary variables

Laboratory parameters will be analyzed descriptively. Results will be displayed by summary statistics and as change from baseline.

A descriptive analysis will be performed for the number of patients with laboratory parameters outside of the normal ranges.

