9.3.2 Outcomes? (e.g. International Classification of Diseases (ICD), Medical Dictionary for Regulatory Activities (MedDRA))				9.7
9.3.3 Covariates and other characteristics?				9.7
9.4 Is a linkage method between data sources described? (e.g. based on a unique identifier or other)				

Comments:

--

Section 10: Analysis plan	Yes	No	N/A	Section Number
10.1 Are the statistical methods and the reason for their choice described?				9.7
10.2 Is study size and/or statistical precision estimated?				9.7
10.3 Are descriptive analyses included?				9.7
10.4 Are stratified analyses included?				9.7
10.5 Does the plan describe methods for analytic control of confounding?				
10.6 Does the plan describe methods for analytic control of outcome misclassification?				
10.7 Does the plan describe methods for handling missing data?				9.7
10.8 Are relevant sensitivity analyses described?				9.7

Comments:

Section 11: Data management and quality control	Yes	No	N/A	Section Number
11.1 Does the protocol provide information on data storage? (e.g. software and IT environment, database maintenance and anti-fraud protection, archiving)				9.8.3
11.2 Are methods of quality assurance described?				9.8.1
11.3 Is there a system in place for independent review of study results?				9.8.2

Comments:

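### Starters and current users are pooled with study entry as baseline, so change from baseline depends on an unstated user mix and early-event rates understate risk from treatment start

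*Protocol*

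**What the plan says.** **Who enters.** Section 9.2.4: "The study will enroll previously treated hemophilia A patients initiating or currently receiving prophylaxis damoctocog alfa pegol". No quota or stratum for either group is given. Entry requires a negative inhibitor test (9.2.1.1) and no known or suspected contraindication (9.2.1.2).

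**What baseline is.** Section 9.2.5: "The physician documents a first visit that corresponds to the initiation of the observational period (initial visit/baseline) in the eCRF/EDC system". The secondary endpoints in 9.1.2 use the same anchor: "Change in PEG-plasma levels from study start to the end of the study" and "Change in kidney and liver function parameters from study start to the end of the study". Section 9.7.4 says of the laboratory parameters: "Results will be displayed by summary statistics and as change from baseline".

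**Who is analysed.** Section 9.7.1: "All analyses will be performed for the total study population (overall analysis". The person-time rule in that section counts time on prophylaxis without reference to time since first dose.

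**When events count.** Under 11.2, adverse events are documented from the first dose after enrollment. Anything earlier is medical history.

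**What else bears on it.** Table 2 collects each patient's damoctocog alfa pegol history at the initial visit, but no analysis in section 9.7 uses it. In Annex 2, item "10.4 Are stratified analyses included" is answered yes with a pointer to 9.7, and so is item 10.8 on sensitivity analyses. Sections 9.7.1 to 9.7.5 describe neither.

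**The concern.** The study asks whether long-term exposure brings harm, including harm that might point to PEG accumulation. Two of its summaries are hard to read for that purpose.

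First, change from study start is not the same quantity in every patient. In someone starting the product it can be a change from before exposure to on treatment. In someone already on it, it is a change between two on-treatment points, and any shift in a kidney or liver value that occurred before enrollment is already inside the baseline. A single mean over both has no fixed meaning unless the mix is known.

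Second, current users have already passed through the early treatment period. Those who developed an inhibitor are ineligible, and those who stopped after a hypersensitivity reaction are no longer receiving the product and so are not in the cohort. A pooled rate of such events may be read as the risk a patient faces on starting treatment, and it would be too low for that reading.

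**Working it through.** **1. Reproduce the plan's own figure.** Inputs from section 9.5: risk 2%, 50 patients.

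P(at least one event) = 1 − (1 − 0.02)^50 = 1 − 0.98^50 = 0.636, which agrees with the stated 64%.

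**2. Apply it to an event confined to the early treatment period.** Suppose the 2% risk is spent entirely soon after the first-ever dose. Current users then contribute no chance of a case, and the effective sample is the number of new users, n_new. The share of new users is not in the protocol, so a range is assumed:

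| Assumed share of new users | n_new of 50 | 1 − 0.98^n_new |
|---|---|---|
| 100% | 50 | 63.6% |
| 75% | 38 | 53.6% |
| 50% | 25 | 39.7% |
| 25% | 12 | 21.5% |
| 10% | 5 | 9.6% |

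The 64% therefore holds for an early-only event only if all 50 are new users observed from their first dose. For an event whose risk is constant over time on treatment, the mix alone does not reduce it.

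**3. Change from baseline.** Let s be the share of new users among patients with paired samples, L the rise from pre-exposure to steady state, and a the further change on treatment, taken as common to all. Suppose new users are sampled before their first dose and current users enter at steady state:

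pooled mean change = s × (L + a) + (1 − s) × a = s × L + a.

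The quantity of interest for accumulation is a. The pooled mean gives s × L + a, so a cannot be recovered without s and L. For a kidney or liver value with a one-off shift D after starting, already complete in current users at entry, the pooled mean change is s × D. The shift is diluted in proportion to the share of current users.

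**4. Compare the checklist with section 9.7.** Items 10.4 and 10.8 say that stratified and sensitivity analyses are described in 9.7. The section contains an overall analysis, summary statistics, coding rules, missing-data rules and a person-time rule. It contains no stratified or sensitivity analysis.

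**The case against.** **Change is not the only output.** Section 9.7.1 has continuous variables described by absolute value as well as by change, and 9.7.4 adds counts of patients outside normal ranges. Change within a current user also still shows further accumulation. A reader might infer that the study cannot show or rule out accumulation at all, and that does not follow. What stands is that the pooled mean change is confounded and diluted.

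**A PEG magnitude is tempting.** Section 7.2 gives a level of "approximately 0.1 mg/L at steady state in humans". A reader might put this in for L and conclude that, with half new users, the pooled change is 0.5 × 0.1 = 0.05 mg/L without any accumulation. The documents do not support that as an estimate. The figure is a peak, and routine samples need not be peaks. Section 9.3 leaves PEG sampling to the investigator, for instance after a suspicious event, so paired samples are not assured and may be self-selected. Section 9.2.5 does not require the initial visit to precede the first dose. Previously treated patients may also have used another PEGylated product, so a zero starting level is an assumption.

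**The objective is long-term safety.** A reader might infer that all the rates are biased low. That holds only for early events when the target is risk from the first-ever dose. Events and exposure are already counted from enrollment, so no event-free time from before entry is designed into the rates.

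**The analysis plan may add the split.** Section 9.7.1 defers statistical detail to it and does not forbid subgroup tables. Even so, the protocol itself fixes the anchor at study start, commits only to the overall analysis, and claims stratification in a section where there is none.

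**Item 8.1 of the checklist** might also look false. It gives collection of data on effect modifiers as an example, and Table 2 collects product history, so its yes is defensible.

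**Conclusion.** The concern holds in a bounded form. Followed as written, change from baseline in PEG, kidney and liver values mixes baselines that may be pre-exposure with on-treatment ones, and the pooled mean depends on a user mix that the protocol neither controls nor states. Pooled rates of early immune events understate the risk from treatment start. Section 9.9 names selection bias in general terms but not prior exposure or delayed entry.

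The size of either effect cannot be computed from the protocol. The drop from 64% to about 40% is an illustration. It assumes 25 new users among 50, a 2% risk confined to the early period, no risk left in current users, and observation of new users from their first dose. The checklist mismatch on items 10.4 and 10.8 needs no assumption. This should be corrected, but it does not empty the study of information, because absolute values, out-of-range counts and on-treatment change remain available.

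**What to change.** - In 9.7.1, classify each patient as a new or current user at entry from the damoctocog alfa pegol history in Table 2.
- In 9.7.3 and 9.7.4, report rates of adverse events of special interest, and laboratory and PEG changes, for each group alongside the overall result.
- In 9.7.4, describe PEG accumulation by change between on-treatment samples. Use laboratory values from before the first dose as baseline only where they are already recorded. Table 2 does not list them for current users, so requiring them would mean extra retrospective collection.
- In 9.9, state that current users are a selected group with delayed entry.
- In Annex 2, make items 10.4 and 10.8 match section 9.7. The split makes 10.4 true. Item 10.8 needs either a described sensitivity analysis or a changed answer.

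The cost is wording and a few more tables, with no new visits or procedures. The drawback is wider subgroup intervals and sparse counts. At 2% risk in 50 patients only 50 × 0.02 = 1 event is expected overall, so the split rates would be descriptive and often empty.

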9.2.5 Visits

The physician documents a first visit that corresponds to the initiation of the observational period (initial visit/baseline) in the eCRF/EDC system. Follow-up visits occur during routine practice – in this non-interventional study, the exact referral dates for those visits are not defined in the study protocol. After the initial visit, data collection will continue for a minimum of 48 months. Data collection will continue after 48 months for those patients who are still within the overall study period (for patients initiating follow-up in the first years of the study). Each visit or assessment, as well as each AE, recorded in the patient diary is to be documented in the eCRF/EDC system. The data to be collected, where they are available as part of routine practice, are summarized in [Table 2](#).

Enrollment/Initial visit

Once a patient is deemed eligible for inclusion, the physician will inform the patient and legal representative (where applicable) about the study. If the patient is interested in participating, the physician will ask the patient (and, if appropriate, the legal representative) to sign the informed consent form (see section [10.4](#)). After patients have been enrolled in the study, baseline information is recorded during this initial visit.

Follow-up data collection period

The follow-up assessments will be completed in the eCRF/EDC system. These assessments do not require the scheduling of any additional visits outside of the standard of care.

Due to the observational nature of the study, no specific follow-up visits can be scheduled, and it is unknown when a patient will come for the next visit. Thus, data collection will occur continuously throughout the patient's observational period, i.e. each visit or assessment is to be documented in the eCRF/EDC system.

In case a patient is seen by more than one physician (e.g., the patient is monitored by a physician other than the initial treating physician), the initial treating physician should make every effort to collect information on visits that took place (and results that were obtained) outside the treating physician's site. For example, by communicating with the other physician or by having the patient/legal representative obtain a letter with detailed information and results (e.g. ARs, medications given, procedures performed).

End of observation and final safety follow-up

The final data collection (end of observation) should be after 50 patients have been followed-up for a minimum of 4 years.

Final collection of safety data (e.g. AEs) will occur up to 30 days after the last dose of damoctocog alfa pegol within the study period.

Lost to follow-up

A patient is considered ‘lost to follow-up’ if no further information can be expected from the patient at a given point in time.

If no information had been obtained from a patient within 12 months from the last data collection time point, site personnel are requested to apply due diligence (within the applicable legal limits) to contact patients and ascertain the reason for an absence of information. In case no information can be obtained, the site should confirm that the patient is lost to follow-up and document the end of observation.

Table 2: Overview of information collected during the initial visit and at subsequent follow-up visits

	Enrollment / Initial visit	Follow-up visit (including end of observation)
Eligibility assessment ³	X	
Date of visit	X	X
Date of informed consent	X	
Demographic data ⁴ (e.g. date of birth or age; ethnicity, race)	X	
Hemophilia disease history, mutation genotype	X	
Hemophilia treatment history (including Damoctocog alfa pegol history, if any)	X	
Medical history and concomitant diseases	X	
Physical examination (e.g. weight, height, vital signs)] ⁵	X	X
Prior and concomitant medications	X	X

³ Including confirmation of eligibility criteria or documentation of reason for non-enrolment, where applicable (see 9.2.4)

⁴ The availability of demographic variables is likely to vary per country according to legal and ethical regulations. Race will only be collected where legally permitted

⁵ If available (i.e. if conducted during routine clinical examination).

	Enrollment / Initial visit	Follow-up visit (including end of observation)
Currently prescribed damoctocog alfa pegol regimen	x	x
Damoctocog alfa pegol dose/regimen changes, treatment switches		x (continuous collection)
Damoctocog alfa pegol pharmacokinetic analysis ⁵	x	x
Adverse events, Serious adverse events and Adverse reactions (includes systematically collected AEs and AEs of special interest) ^{6,7}	x (continuous collection)	
FVIII inhibitor ⁵	x	x
Biochemistry ^{5,8}	x	x
Urinalysis ^{5,9}	x	x
PEG-plasma ^{5,6}	x	x
Neurological assessment ^{5,10}	x	x
Number of bleeding episodes	x	x
Reason(s) for end of observation		x (at occurrence)

